## **SECTION Q: CERTIFICATE OF CONFIDENTIALITY**

In 2017 the NIH updated its policy for issuing [\*\*Certificates of Confidentiality\*\*](#). Under the policy, all **eligible** research studies funded by the NIH are automatically issued a certificate of confidentiality. Investigators whose research is not funded or supported by the NIH may request and obtain from the NIH a Certificate of Confidentiality. Investigators who request and receive Certificates must follow the NIH and PHS policies governing such certifications.

YES	NO	
		Is your research funded by the NIH and eligible for a Certificate of Confidentiality?
		If your research is not funded by the NIH, will you be applying for a Certificate of Confidentiality?

## **SECTION R: PRIVACY**

### **Describe how you will protect the privacy of subjects (e.g. where will consent procedures take place, if interviews or other interventions, where will these procedures take place)**

Privacy of participants will be protected by conducting all in-person interactions in a semi-private or private space. No personally identifiable information will be discussed in common areas.

**Photos/Videos** – Participants will be asked to confirm their preference on the collection of photo/video during testing via a check-off box in the consent form.

- All photo/video will not contain participant names or other identifiable information and will be stored on an encrypted password protected SharePoint folder with access limited to the research team.
- Any photo/video that captures a participant's face or other identifiable landmark will be blurred out if used for publications, presentations, training purposes, or promotional purposes.

**Personal Health Information** – Any medical records obtained during the course of the study will be de-identified and labeled only with a letter/number combination for each participant.

## **SECTION S: MONITORING STUDY DATA**

### **How will data be monitored?**

**Note:** The Data and Safety Monitoring Plan should be tailored to the nature, size, and complexity of the research protocol, the expected risks of the research, and the type of subject population being studied.

	Principal Investigator
	Monitor/Monitoring Group
	Data and Safety Monitoring Board (DSMB) Note: The DSMB Charter must be submitted with this Application. For more information regarding a DSMB, please refer to the NIH website .

### **Describe the plan for monitoring study data. This should include a description of how data will be collected and analyzed as the project progresses to assure the appropriateness of the research, its design, and subject protections.**

Data will be collected and de-identified (using participant ID number only). This de-identified data will be processed and analyzed by the PI and research team (Section E).

Occurrences of adverse events will be described and recorded and any medical attention sought will be documented. If a deviation in data collection/usage, adverse or unanticipated event involving risks to participants or others, or a breach in confidentiality is suspected or found, the study will be halted until a resolution is determined in accordance with the IRB. The following definitions will be applied to the present study to monitor adverse events:

**Adverse Event:** Any untoward or unfavorable physical or psychological occurrence in a participant, including any abnormal sign (e.g., abnormal physical exam or laboratory finding),

symptom, or disease temporally associated with participation in the research, whether or not considered related to participation in the research. The PI will be notified when any adverse event is identified and will report this to the IRB.

**Serious Adverse Event:** Any adverse event that:

- i. results in death
- ii. is life-threatening (places the participant at immediate risk of death)
- iii. results in hospitalization
- iv. results in a persistent or significant disability/incapacity
- v. results in a congenital anomaly/birth defect
- vi. may jeopardize the participant's health and may require medical or surgical intervention to prevent one of the other outcomes listed in this definition.

**Unexpected Adverse Event:** Any adverse event occurring in one or more participants, the nature, severity, or frequency of which is not consistent with either:

- i. the known or foreseeable risk of adverse events associated with the procedures involved in the research that are described in (a) the protocol-related documents, such as the IRB-approved protocol, any applicable investigator brochure, and the current IRB-approved informed consent document, and (b) other relevant sources of information, such as product labeling and package inserts.

## **SECTION T: HIPAA**

### **Health Insurance Portability and Accountability Act**

YES*	NO	
		
Is this research being conducted in a covered entity?  The following BU CRC Departments are considered covered entities:
 
 
• Sargent College Rehabilitation Services 
 
◦ Physical Therapy Center at the Ryan Center for Sports Medicine and Rehabilitation
 
◦ Sargent Choice Nutrition Center
 
 
 
• The Daniels Institute
 
• Boston University Health Plan
 
 
*If YES, contact the IRB office for assistance.

## **SECTION U: FAMILY EDUCATIONAL RIGHTS AND PRIVACY ACT (FERPA)**

**(FERPA):** FERPA is the federal law that protects the privacy of student education records. Research funded by the Department of Education or research conducted in educational institutions that receive funds from the Department of Education (for research or other purposes) must comply with FERPA.

YES*	NO	
		
Does this study involve collection of information from student school/university records? *If YES, refer to the following websites for guidance on FERPA:
 
 
• http://www.bu.edu/researchsupport/compliance/human-subjects/
 
• http://www.bu.edu/reg/general-information/ferpa/
 

		
 
• http://www2.ed.gov/policy/gen/guid/fpcos/ferpa/index.html
 
 
If FERPA applies, you must complete the box below:

In accordance with FERPA, written consent must be obtained to access student records. The consent must:
 
 
• Specify the records that may be disclosed
 
• State the purpose of the disclosure
 
• Identify the person or class of parties to whom the disclosure can be made
 
		
 YES (REQUIRED)	
I confirm that I will comply with the FERPA policy that is in place at the educational institution where I am conducting my research. This includes, if applicable, the requirements for written agreement when requesting a waiver of consent for personally identifiable information. If an agreement is required, this agreement must be submitted to the IRB.
	

## **SECTION V: PROTECTION OF PUPIL RIGHTS AMENDMENT (PPRA):**

PPRA is a federal law that affords certain rights to parents of minor students with regard to surveys that ask questions of a personal nature. Research funded by the Department of Education or research conducted in educational institutions that receive funds (for research or other purposes) from the Department of Education must comply with the PPRA.

YES*	NO	
		
Does PPRA apply to this study? If YES, refer to the following websites for guidance:
 
 
• http://www2.ed.gov/policy/gen/guid/fpcos/ppra/index.html
 
• http://www.bu.edu/researchsupport/compliance/human-subjects/
 
 
If PPRA applies, you must complete the box below:

In accordance with PPRA, written parental consent must be obtained prior to subjects participation in the study.
		
 YES (REQUIRED)	
I confirm that I will comply with the PPRA policy that is in place at the educational institution where I am conducting my research.
	

## **SECTION W: CLINICAL TRIALS REGISTRATION:**

The Food Drug and Administration Amendments Act (known as FDAAA 801) requires that “applicable clinical trials” be registered and have results reported on clinicaltrials.gov. In addition, the International Committee of Medical Journal Editors (ICJME) and the National Institutes of Health (NIH) also have requirements for registration. Please see box below to determine if your study requires registration in accordance with either FDAAA 801, ICJME, or NIH.

YES	NO	FDAAA 801 Requirements
		
Does your study meet the definition of an applicable clinical trial (ACT) and require registration AND results submission in accordance with FDAAA 801? ACTs include:
 
 
• Trials of drugs and biologics: Controlled clinical investigations, other than phase 1 clinical investigations, of drugs or biological products subject to Food and Drug Administration (FDA) regulation
 
• Trials of devices (see note): 1) Controlled trials with health outcomes of devices subject to FDA regulation, other than small feasibility studies, and 2) pediatric post-market surveillance required by FDA
 

		
Note: If your study meets the requirement for registration and reporting, you must submit the National Clinical Trial (NCT) Identifier # to the IRB prior to IRB approval. NCT #:

YES	NO	
ICMJE Requirements
 
  Does your study meet the definition of a clinical trial and require registration in accordance with ICMJE?
 
Note: If your study meets the requirement for registration, you must submit the National Clinical Trial (NCT) Identifier # to the IRB prior to IRB approval. NCT #:
 
Phases 1 and 2 of this study do not meet the definition of a clinical trial. However, some research activities conducted as part of Phase 3 of this study (Clinical Training Studies) may qualify. Because we are currently in the early development stages of this device, we have not finalized the technology that would be used in potential clinical trials. When the technology has been developed and appropriately tested, we will register any Phase 3 procedures of this study that would be defined as a clinical trial in accordance with ICMJE.

YES	NO	
NIH Requirements
 
  Does your study meet the definition of an applicable clinical trial and require registration AND results submission in accordance with NIH?
 
For more information on this policy please refer to:
 
 
• NIH Policy on the Dissemination of NIH-Funded Clinical Trial Information
 
• Checklist
 
 
Note: If your study meets the requirement for registration and reporting, you must submit the National Clinical Trial (NCT) Identifier # to the IRB prior to IRB approval. NCT #:

Statistical Analysis Plan

Protocol 5715: Effects of an Overground Propulsion Neuroprosthesis in
Community-dwelling Individuals After Stroke

Clinical Trial Number: NCT06459401

1/3/2024

Objective

The primary objectives of this study were to i) determine the immediate and retained effects of overground walking with the propulsion FES neuroprosthesis and ii) evaluate the impact of neurostimulation timing on individual propulsion biomechanics.

Study Participants

Ten individuals in the chronic phase of stroke recovery (2 female; 53 ± 11 years old; 8 ± 1 years poststroke) completed this study. Each study participant completed one session that consisted of i) neurostimulation tuning and exposure, ii) overground gait training with propulsion FES, and iii) pre-session and post-session evaluations. Mean \pm standard error (SE) are reported for all conditions and effect sizes (ES) are calculated using the pooled standard deviation (SD), unless otherwise specified. Medians are reported for all percent changes to account for outliers that may occur during the calculation of the percent change from baseline for those with small baseline values.

Inclusion criteria consisted of age at least 18 years, stroke chronicity greater than 6 months, ability to walk independently with or without an assistive device for at least 30 meters, and passive range of motion of the paretic ankle reaching neutral (90 degree angle). Participants were excluded if they had history of lower extremity joint replacement, metal implants beneath neurostimulation sites, and/or inability to communicate with the study team. All study procedures were approved by the Institutional Review Board at Boston University. Medical clearance was obtained for all study participants from their primary healthcare providers. All participants provided written informed consent.

Study Design

This study was designed to evaluate the immediate and carryover (i.e., post-session retention) benefits of walking with the propulsion FES neuroprosthesis. Before and after the session, unassisted comfortable and fast walking speeds were assessed using the 10-meter Walk Test (10mWT). Kinetic data were collected at 2000 Hz from six floor-embedded force platforms (Bertec Corp., Columbus, Ohio). Kinematic data were collected at 200 Hz using 18 optical motion capture cameras (Oqus, Qualisys AB, Göteborg, Sweden). Prior to data collection, the propulsion FES neuroprosthesis was tuned for each participant. Participants then completed two 5-minute treadmill walks at a comfortable speed to become accustomed with each of the two plantarflexor neurostimulation onset timing profiles and the transitions between walking with and without FES assistance. Participants then completed five sets of overground walks with the neuroprosthesis,

each set consisting of eight walks across a ten-meter walkway. These sets alternated between unassisted (sets 1, 3, 5) and assisted (sets 2 and 4) walking, with each assisted set assessing one of the two plantarflexor neurostimulation onset timings in a randomized order. Rest breaks were provided as needed after each walking trial, and participants wore a fall-prevention harness without bodyweight support for safety during all walks.

Data Processing and Analysis

Pre-session and post-session walking speeds were calculated as the average of three 10mWT trials. Peak propulsion was calculated as the maximum anteriorly directed ground reaction force normalized by bodyweight. Propulsion symmetry was calculated as the percentage of paretic propulsion impulse (i.e., the positive integral of the anterior ground reaction force) to the sum of the propulsion impulses of both limbs. All study data were processed using commercial motion analysis software (Visual 3D, C-Motion Inc., Boyds, MD) and a computing platform (MATLAB, The MathWorks Inc., Natick, MA). Kinetic and kinematic data were filtered using a fourth-order Butterworth lowpass filter with a cutoff frequency at 10 Hz. Timeseries data were stride-segmented by initial foot contact and normalized to a percentage of the gait cycle. Point metrics from the timeseries data were calculated in MATLAB by averaging all strides within each condition.

Commercial statistical software (SPSS Version 28, IBM Corp.) was used to conduct all statistical analyses with alpha set to 0.05. Normality of each variable's distribution was assessed using the Kolmogorov-Smirnov test. Depending on the normality of each variable, either paired t-tests or Wilcoxon signed-rank tests were used to determine i) immediate changes (i.e., from unassisted walking to propulsion FES-assisted walking), ii) differences in immediate changes between timing profiles (i.e., non-preferred timing vs. preferred timing), iii) retained changes in unassisted walking (i.e., from pre-session post-session). Descriptive statistics are reported as mean \pm standard deviation (SD). Results are reported as mean \pm standard error (SE), unless indicated otherwise. Percent changes ($\% \Delta$) are reported as medians. P-values (p) and standardized effect sizes (ES) are reported for each analysis.

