This visit will last **up to 3 hours**. Participants who have had a stroke will be asked to complete a medical history and physical examination to assess neurological complications and medical comorbidities, stroke-specific weakness/balance impairment, cognitive or behavioral issues, and communication issues. For example, participants will be asked to complete the following:

- a. NIHSS Cognitive Screen (only Question 1b and 1c)
- b. Medical History
- c. Walking and range of motion assessments (Functional Gait Assessment, Fugl-Meyer)
- d. Assessments to understand participant's physical activity and comfort performing various tasks (Activities-Specific Balance Confidence scale, International Physical Activity Questionnaire (IPAQ))
- e. Overground comfortable walking speed (CWS) and fast walking speed (FWS) assessed using three 10-meter walk tests for each speed
- f. Overground long-distance walking ability using the 6-minute walk test
- g. Brief, harnessed, treadmill walking

We may also collect sensor data (e.g. movement-related) and/or vitals (e.g. heart rate and blood pressure) during the visit.

If the individual is deemed eligible, they will review and sign the study's Informed Consent Form and a HIPAA Authorization Form that allows their physician to disclose protected health information for research purposes, which is necessary to obtain medical clearance and communicate with the physician's office during the course of the study, if necessary. Procedures for reviewing and signing these forms are described under the primary screening visit in Section L, Part (a).

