**Training Visits (2-3 visits per week for up to 12 weeks):**

Participants will be asked to come in for 2-3 training visits per week for up to 12 weeks for training visits. Each visit will be no more than **3-4 hours** in total duration.

The purpose of the training visits is to understand the therapeutic effects of training with exosuit/FES assistance (Active Training condition) compared to training without the exosuit or FES system (Control Training condition). Prior to beginning training, participants will be *randomly assigned* to either Active Training or Control Training. Randomization procedures will be the same for Group 1 (current in-clinic rehabilitation) and Group 2 (no in-clinic rehabilitation). Both training conditions (active and control) will implement gait training within a range of moderate-to-high intensity walking speeds.

Utilizing concepts in motor learning, training is designed to be high intensity and task-specific. Training will progress based on the participant's capacity by increasing variability and complexity of training environments. An example training progression might begin within controlled environments such as a quiet, temperature-controlled laboratory space. Over the course of training, activities will progress to more open, real-world environments such as a common hallway or an open gym where external factors such as noise, foot traffic, curved paths, and other distractions approximate those of real-world scenarios.

Gait training at fast walking speeds typically involve exercising in higher intensities. From a cardiovascular standpoint, as previously described, we will aim to keep participants within a range of 60 - 80% of their heart rate reserve, computed using their age-predicted heart rate (HR) maximum calculation ( $HR_{max} = 208 - [0.7*age]$ )x. If a participant is taking beta blockers, HR parameters will be reduced by 10 bpm. These parameters are adapted from a clinical trial that implemented stepping practice in stroke at high intensities xii.

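### The SAP words the pre- to post-session change as a retained effect of FES, but with no no-FES session or arm the change cannot be attributed to FES

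*SAP*

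**What the plan says.** The SAP's Objective section sets out, as part of primary objective (i), to "determine the immediate and retained effects of overground walking with the propulsion FES neuroprosthesis". The Study Design section repeats the idea as a design purpose: "This study was designed to evaluate the immediate and carryover (i.e., post-session retention) benefits of walking with the propulsion FES neuroprosthesis". Both sentences name FES walking as the source of whatever is retained.

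The design behind this is a single group: "Ten individuals in the chronic phase of stroke recovery" took part, and "Each study participant completed one session that consisted of" tuning and exposure, overground training with FES, and evaluations before and after (SAP, Study Participants). The five overground sets alternate between unassisted (1, 3, 5) and assisted (2, 4), "with each assisted set assessing one of the two plantarflexor neurostimulation onset timings in a randomized order" (SAP, Study Design).

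The retention analysis is item iii in the SAP's Data Processing and Analysis section: a paired t-test or Wilcoxon signed-rank test, at alpha 0.05, of "retained changes in unassisted walking (i.e., from pre-session post-session".

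The protocol does describe a no-device comparator. In Section L, Training Visits, Active Training is to be judged "compared to training without the exosuit or FES system (Control Training condition", with random assignment. That belongs to the multi-week Phase 3 training studies and is not part of this SAP.

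**The concern.** To call a post-session change a retained effect of FES is to say that it would not have occurred, or would have been smaller, had the same session been done without FES. That needs a no-FES counterpart, and the SAP has none. Everyone receives both timings, so randomising their order can compare one timing with the other but gives no contrast against no FES.

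Retention is half of a stated primary objective and gets its own p-value. As worded, a significant item iii would be read as evidence of FES carryover when it could be warm-up or practice. A non-significant one could be read as evidence against carryover when fatigue may have masked it. The p-value supports neither reading; it speaks only to whether walking changed over the session.

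The immediate effect (assisted against unassisted sets) has a within-session comparator and is not affected by this point.

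**Working it through.** The documents give no sample-size calculation, effect size or SD for the retention analysis, so there is no stated figure to reproduce. The point is structural; the arithmetic only shows what follows from it.

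**What lies between the two evaluations (SAP, Study Design).** Each person did two 5-minute treadmill walks that introduced both timings and the transitions on and off FES. Each then did 5 × 8 = 40 ten-metre walks:

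- unassisted: 3 × 8 = 24 walks (240 m, 24/40 = 60%)
- assisted: 2 × 8 = 16 walks (160 m, 16/40 = 40%)

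Most of the overground walking between the pre- and post-session tests was therefore without FES.

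**What item iii estimates.** Let F be the mean carryover due to FES and W the mean change that the rest of the session would produce (warm-up, practice, fatigue). Then

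E(post − pre) = F + W.

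The paired test addresses F + W = 0. A no-FES session or arm would estimate W; without one there is one equation and two unknowns. The 0.05 level protects against a false claim of change, not against a false claim of an FES effect.

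**Illustration.** Assumptions: paired t-test, n = 10, two-sided 0.05 (the SAP does not state sidedness and also allows Wilcoxon), shifts in units of the SD of the change. With 9 df the critical value is 2.262, and the test statistic is noncentral t with noncentrality d√10, where d = F + W. The values of F and W are assumed.

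| F (FES) | W (non-FES) | d = F + W | P(significant) |
|---|---|---|---|
| 0 | 0 | 0 | 5% |
| 0 | +0.3 | 0.3 | 14% (0.136) |
| 0 | +0.5 | 0.5 | 29% (0.293) |
| 0 | +0.8 | 0.8 | 62% (0.616) |
| 0 | +1.0 | 1.0 | 80% (0.803) |
| 0.8 | 0 | 0.8 | 62% (0.616) |
| 0.8 | −0.3 | 0.5 | 29% (0.293) |
| 0.8 | −0.5 | 0.3 | 14% (0.136) |

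A simulation of 400,000 runs gave 0.137, 0.293, 0.617 and 0.803 for d = 0.3, 0.5, 0.8 and 1.0. Rows with the same d have the same probability: no result of the test can tell F = 0, W = 0.8 from F = 0.8, W = 0.

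**Reading back from a result.** The smallest significant observed change is 2.262/√10 = 0.715 SD. Taking that as the observed change, the implied FES part is 0.715 − W. For W from −0.5 to +1.0 SD it runs from 0.715 + 0.5 = +1.22 to 0.715 − 1.0 = −0.28 SD, so over that assumed range the sign of the FES part is not identified.

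**The case against.** Several points can fairly be made in the plan's defence.

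- *The analysis wording is neutral.* Item iii speaks of changes in unassisted walking and attributes nothing. This is true, but it does not correct the objective or the design statement, which do. The SAP's objective claims more than its own analysis measures.
- *The intervention may be the whole session.* The SAP describes all five sets, unassisted ones included, as walks with the neuroprosthesis, so practice within the session could count as part of the treatment. The wording allows this reading, but the pre- to post-session change is then just as uncontrolled.
- *Rival explanations are limited.* Participants averaged 8 years poststroke, so spontaneous recovery within a session is not credible. Rest breaks were available after each walk. Secondary Screening (Protocol, Section L) includes comfortable and fast speeds "assessed using three 10-meter walk tests for each speed" and brief harnessed treadmill walking, so first-time learning of the test or harness is probably a smaller part. All of this stands, but none of it removes warm-up, practice or residual fatigue within the session.
- *The numbers are generic.* They are the power curve of a ten-person paired t-test under assumed shifts. The sign result needs W to be able to exceed 0.715 SD, and it ignores sampling error. A null result is weak in any case, with 62% power at 0.8 SD and no fatigue. All of this is correct; the figures illustrate the point and do not establish it.
- *Evidence is staged.* The protocol places the controlled training comparison in Phase 3, and an uncontrolled single-session study is a legitimate exploratory step. Agreed: the fault is in the claim, not in the choice of design.

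**Conclusion.** The concern holds and should be fixed. The retained half of primary objective (i) and the design statement ascribe to FES a change that this design cannot attribute to it. This follows from the SAP's own description (one session each, FES for everyone, only timing order randomised, a paired pre- to post-session test) and depends on no assumed number.

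The size and direction of the bias are unknown. The illustrative 14% to 80% false-attribution range, and the fall in detection from 62% to 29% or 14% under fatigue, rest on assumed shifts in SD units and a two-sided t-test. What item iii can support is a statement about change in unassisted walking over the session.

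**What to change.** Restate the retained part of objective (i), the design statement and any conclusion drawn from item iii as: *pre- to post-session change in unassisted walking after one session of mixed assisted and unassisted walking*. Do not describe it as a retained effect or carryover benefit of FES. Add a limitation: *there was no no-FES comparator, so the change cannot be attributed to FES, and the direction of any bias is unknown*.

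Set 5 minus set 1 may be reported as a descriptive supplement only. It too is uncontrolled, set 1 already follows the treadmill FES exposure, and the difference does not isolate FES.

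The cost is wording and one limitation statement, with no change to tests or data. The price is a weaker claim for the retained half of the objective. The SAP reports the ten participants as having completed the study, so a comparator would mean new data. For scale, at 80% power and two-sided 0.05, with assumed effects of 0.5, 0.8 or 1.0 SD, a parallel no-FES arm would need about 63, 25 or 16 per arm (normal approximation, SD of the change score). A crossover with a no-FES session would need about 34, 15 or 10 people (SD of the within-person difference in change). That is a matter for a later study and is not needed to correct this SAP.

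### With ten participants and paired contrasts, must the SAP say which quantity is checked for normality and promise a confidence interval for each change?

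*SAP*

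**What the plan says.** The SAP's Study Participants section reports a completed sample: "Ten individuals in the chronic phase of stroke recovery", each seen in one session. In Data Processing and Analysis the significance level is "alpha set to 0.05", and the distribution check is described as follows: "Normality of each variable's distribution was assessed using the Kolmogorov-Smirnov test". The choice of test comes next: "Depending on the normality of each variable, either paired t-tests or Wilcoxon signed-rank tests were used". It covers three families of within-participant contrasts:

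- the immediate effect, described as "immediate changes (i.e., from unassisted walking to propulsion FES-assisted walking";
- the difference in that effect between the two stimulation timings;
- the retained change from before to after the session.

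Reporting is covered in two places. Study Participants says that the mean and "standard error (SE) are reported for all conditions and effect sizes (ES) are calculated using the pooled standard deviation (SD), unless otherwise specified". Data Processing and Analysis gives descriptive statistics as mean and SD, and results as mean and "standard error (SE), unless indicated otherwise". It adds: "P-values (p) and standardized effect sizes (ES) are reported for each analysis". Percent changes are summarised by medians. No confidence interval is named in the SAP or the protocol.

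**The concern.** A paired t-test assumes that the within-participant differences are roughly normal. It assumes nothing about the marginal distribution of each condition. The variables that Data Processing and Analysis defines (walking speed, peak propulsion, propulsion symmetry) are values per condition or time point, so a reader may take the check to be on the wrong quantity. The two choices can disagree: skewed baselines can go with normal changes, and the reverse.

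The second worry is precision. An SE attached to a condition is not the SE of the change being tested. With ten people, a non-significant retained change can be compatible with a large one, and a p-value with a pooled-SD effect size does not show that. If the gap were harmful, the stakes would be lost power from a badly chosen test and a null retention result read as evidence of no retention.

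**Working it through.** **Inputs.** n = 10 (SAP, Study Participants) and alpha = 0.05 (SAP, Data Processing and Analysis; taken as two-sided, since the side is not stated). The documents give no SD of change, no within-participant correlation, and no power or interval figure. There is therefore no stated figure to reproduce, and everything below that depends on a distribution or a correlation is an assumption.

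**1. What an interval would show.** The half-width is t(0.975, 9) × SD of differences / √10 = 2.262 / 3.162 = 0.715 SD of the differences. Relative to the estimate, the limits are 1 ± 2.262 / t, where t is the observed statistic.

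- p = 0.05: t = 2.262, limits 0 to 2.00 times the estimate.
- p = 0.20: t = 1.383, 2.262 / 1.383 = 1.64, limits -0.64 to 2.64 times the estimate.

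So the interval is informative. For a paired t result with an exact p-value, a reader can also recover it, because SE of change = |mean change| / t on 9 df. That route is closed for a Wilcoxon result.

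**2. Condition SE against SE of the change.** If the two conditions have equal SDs and correlation r, the ratio of condition SE to SE of change is 1 / √(2(1 - r)).

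| r (assumed) | 0 | 0.3 | 0.5 | 0.7 | 0.8 | 0.9 | 0.95 |
|---|---|---|---|---|---|---|---|
| ratio | 0.71 | 0.85 | 1.00 | 1.29 | 1.58 | 2.24 | 3.16 |

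The two can differ either way. No p-value in the plan is computed from the condition SE, so this affects how a table is read and not whether a test is valid.

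**3. Does it matter which quantity is checked?** Two rules were simulated at n = 10 with the exact Wilcoxon test. One rule uses Wilcoxon if either condition fails the check. The other uses it if the differences fail. The Kolmogorov-Smirnov test had the Lilliefors correction (5% critical value 0.262) unless stated otherwise.

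Type I error, conditions rule against differences rule:

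- normal differences: 0.048-0.051 against 0.048-0.053;
- exponential differences: 0.097-0.098 against 0.094-0.096;
- lognormal differences (sigma 0.8): 0.122-0.124 against 0.119-0.121.

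The rules are nearly identical. Where skew pushes the error above 0.05, both exceed it alike, so moving the check to the differences does not cure that.

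Power at a standardised paired effect of 0.8: with normal differences it was 0.607-0.619 against 0.612-0.620. With right-skewed differences and a normal baseline (SD of differences 0.3 times the baseline SD):

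| Differences | Effect relative to long tail | KS critical value | Check conditions | Check differences | Gain from checking differences |
|---|---|---|---|---|---|
| Exponential | same direction | 0.262 | 0.765 | 0.843 | +0.078 |
| Exponential | opposite | 0.262 | 0.639 | 0.616 | -0.023 |
| Lognormal | same direction | 0.262 | 0.878 | 0.976 | +0.098 |
| Lognormal | opposite | 0.262 | 0.699 | 0.669 | -0.030 |
| Exponential | same direction | 0.409 (uncorrected) | 0.763 | 0.765 | +0.002 |
| Lognormal | same direction | 0.409 (uncorrected) | 0.870 | 0.880 | +0.010 |

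The sign of the gain depends on the direction of the skew, which the documents do not indicate. Its size depends on whether the correction is applied, which the SAP does not state. With the uncorrected value the differences fail the check in only 0.4% (exponential) to 1.1% (lognormal) of samples, so both rules almost always give the t-test. With normal differences the rules chose different tests in 12-42% of datasets, but the significance decision changed in only 0.2-2.6%.

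**The case for a change.** The strongest case for a change is the interval. The SAP's objectives are to determine immediate and retained effects, which are questions of size. Ten pairs leave wide uncertainty, and the only SE explicitly tied to anything is the condition SE. A retained change with p = 0.20 is compatible with no effect and with one more than twice that observed. Adding intervals needs one sentence and a few output columns.

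Most of this stands as advice on presentation: the omission is real and an interval would serve the reader. It does not show a defect in the analysis. The contrasts are correctly paired, both tests suit paired data, and an interval from the same pairs leaves every p-value as it is. The omission is also less clear-cut than it looks. Data Processing and Analysis separates descriptive statistics (mean and SD) from results (mean and SE), straight after listing analyses that are all of changes. If results means those changes, the t-interval is the mean ± 2.262 × SE and the ratio table above does not apply. The Study Participants wording points the other way, so the text is ambiguous.

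On the distribution check, the wording is again open and not wrong. An analyst running a paired t-test would ordinarily look at the differences, and the timing contrast is already a difference of changes. The SAP also describes a finished study in the past tense. Naming a single test in advance is no longer possible, and choosing tests afresh on collected data would add analytic freedom.

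**Conclusion.** No change to the plan follows. The SAP leaves two details unstated: which quantity was checked for normality, and whether an interval accompanies each paired change. Neither makes a stated test or figure wrong. The type I error differs by about 0.003 between the two readings of the check. The power difference ranges from about -0.03 to +0.10 in the skewed scenarios tried, is negligible with normal differences, and is at most about 0.01 with the uncorrected critical value. No general power loss can be claimed. These sizes rest on assumed distributions, a standardised effect of 0.8 and, for the skewed power table, a ratio of 0.3 between the SD of differences and the baseline SD. The SE ratios rest on equal condition SDs and an assumed correlation. The conclusion itself rests on the text: the tests are paired, valid and reproducible under either reading, and the missing interval can be supplied at reporting without altering any test result.
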